6.4.3. Survival Follow-Up

Once a subject has confirmed GVHD progression or starts a new GVHD therapy, the subject moves into the survival follow-up period and should be contacted by telephone, email, or visit at least every 8 weeks (\pm 7 days) to assess for new GVHD therapy and survival status until death, withdrawal of consent, or the end of the study, whichever occurs first.

6.5. Unscheduled Visits

Unscheduled visits may be held at any time at the investigator's discretion, and appropriate clinical and laboratory measurements performed based on AEs or other findings.

7. CONDUCT OF STUDY ASSESSMENTS AND PROCEDURES

7.1. Administration of Informed Consent Form

Valid informed consent must be obtained from the study subject before conducting any study-specific procedures using an ICF approved by the local IRB/IEC that contains all elements required by ICH E6 and describes the nature, scope, and possible consequences of the study in a form understandable to the study subject. Local and institutional guidelines for ICF content and administration must be followed; the original signed ICF must be retained by the investigator, and a copy of the signed ICF must be provided to the study subject. The informed consent process for each subject must be documented in writing within the subject source documentation. Subjects of childbearing potential must agree to take appropriate measures to avoid pregnancy in order to participate in the study (see Appendix A).

7.2. Interactive Response Technology Procedure

The IVRS will be contacted to obtain a subject ID number when a subject enters the screening phase. Upon determining that the subject is eligible for study entry, the IVRS will be contacted to obtain study drug assignment. Additionally, the IVRS will be contacted every 28 days to update study drug supply. See Section 5.1.1 for additional information.

7.3. Demography and Medical History

7.3.1. Demographics and General Medical History

Demographic data and a complete medical and medication history will be collected at screening.

7.3.2. Disease Characteristics and Treatment History

A disease-targeted medical and medication history including hematologic malignancy type, current GVHD staging, date of diagnosis, sites of disease, prior anticancer therapy, ablation therapy, prophylaxis therapy, donor type, and other details related to the disease under study will be collected at screening.

7.4. Prior and Concomitant Medications

Prior and concomitant medications will be reviewed to determine subject eligibility. All concomitant medications and measures must be recorded in the eCRF, and any medication received or procedure performed within 30 days before enrollment and up to the end of study will be recorded in the eCRF. The medication record will be maintained after signing the ICF to document concomitant medications, including any changes to the dose or regimen. Concomitant medications include any prescription, over-the-counter, or natural/herbal preparations taken or administered during the study period. Concomitant treatments and/or procedures that are

required to manage a subject's medical condition during the study will also be recorded in the eCRF.

7.5. Safety Assessments

7.5.1. Adverse Events

Adverse events will be monitored from the time the subject signs the ICF. Subjects will be instructed to report all AEs during the study and will be assessed for the occurrence of AEs throughout the study. In order to avoid bias in eliciting AEs, subjects will be asked general, nonleading questions such as "How are you feeling?" All AEs (serious and nonserious) must be recorded on the source documents and eCRFs regardless of the assumption of a causal relationship with the study drug. The definition, reporting, and recording requirements for AEs are described in Section 8.

7.5.2. Physical Examination

The targeted physical examination will be a symptom-directed evaluation conducted by the investigator or a medically qualified designee. The targeted physical examination will include assessment(s) of the body systems or organs, as indicated by subject symptoms, AEs, or other findings. Clinically notable abnormalities that are considered clinically significant in the judgment of the investigator are to be reported as AEs.

7.5.3. Vital Signs

Vital sign measurements include blood pressure, pulse, respiratory rate, body temperature, and body weight. Blood pressure and pulse will be taken with the subject in the recumbent, semirecumbent, or sitting position. Clinically notable abnormalities that are considered clinically significant in the judgment of the investigator are to be reported as AEs.

7.5.4. Eastern Cooperative Oncology Group Performance Status

Eastern Cooperative Oncology Group performance status (Oken et al 1982; Table 8) will be required at screening and will be assessed at other study visits per Table 5. Performance status must be assessed by a medically qualified individual and recorded in the eCRF.

Table 8:	ECOG Performance Status Grades

Grade	Performance Status
0	Fully active, able to carry on all predisease performance without restriction.
1	Restricted in physically strenuous activity but ambulatory and able to carry out work of a light or sedentary nature, eg, light house work, office work.
2	Ambulatory and capable of all self-care but unable to carry out any work activities. Up and about more than 50% of waking hours.
3	Capable of only limited self-care, confined to bed or chair more than 50% of waking hours.
4	Completely disabled. Cannot carry on any self-care. Totally confined to bed or chair.
5	Dead.

7.5.5. Twelve-Lead Electrocardiograms

A 12-lead ECG will be performed during screening with the subject in a recumbent or semirecumbent position after 5 minutes of rest.

The 12-lead ECG will be interpreted by the investigator at the site and will be used for immediate subject management. The decision to include or exclude a subject or withdraw a subject from the study based on an ECG flagged as "Abnormal, Clinically Significant" is the responsibility of the investigator, in consultation with the sponsor's medical monitor, as appropriate.

Electrocardiograms that are identified as abnormal and clinically meaningful compared with the screening assessment should be reported as AEs. For such AEs, the findings of the abnormal ECGs and the corresponding baseline ECG findings must be reported in the eCRF.

An additional ECG will be performed at the EOT visit; additional ECGs may be performed at the investigator's discretion as clinically indicated.

7.5.6. Laboratory Assessments

Blood draws for laboratory assessments will occur at study visits indicated in Table 6. Blood draws will be completed before the subject receives the morning dose of study drug. Specific laboratory assessments are listed in Table 7.

All laboratory assessments will be performed at a local (site) laboratory using institutional best practices. Results and normal reference ranges will be entered into the eCRF.

7.5.6.1. Chemistry

All chemistry assessments will be performed at a local (site) laboratory from blood samples collected using institutional best practices before administration of study drug. Results and normal reference ranges will be entered into the eCRF.

7.5.6.2. Hematology

Hematology assessments, including complete blood count with differential, will be performed at a local (site) laboratory using institutional best practices before administration of study drug. Results and normal reference ranges will be entered into the eCRF.

7.5.6.3. Pregnancy Testing

A serum pregnancy test will be required for all women of childbearing potential during screening and at the EOT visit. Urine pregnancy tests will be conducted only if medically indicated. Urine pregnancy tests will be performed locally. If a urine pregnancy test is positive, then the results should be confirmed with a serum pregnancy test.

If the serum pregnancy test is negative after a urine test was positive, then the investigator will assess the potential benefit/risk to the subject and determine whether it is in the subject's best interest to resume study drug and continue participation in the study.

7.5.6.4. Hepatitis Screening

Subjects with active HBV or HCV infection that requires treatment or who are at risk for HBV reactivation are excluded from the study. At risk for HBV reactivation is defined as hepatitis B surface antigen positive or anti-hepatitis B core antibody positive. Prior test results obtained as part of standard of care before allo-HSCT confirming that a subject is immune and not at risk for reactivation (ie, hepatitis B surface antigen negative, surface antibody positive) may be used for purposes of eligibility, and tests do not need to be repeated. Subjects with prior positive serology results must have negative polymerase chain reaction results. Subjects whose immune status is unknown or uncertain must have results confirming immune status before enrollment as per Table 7.

7.6. Graft-Versus-Host Disease Assessments

7.6.1. Graft-Versus-Host Disease Staging and Grading

Acute GVHD grading will be performed by the investigator on a weekly basis for the first 8 weeks after enrollment, then every 28 days thereafter. Graft-versus-host disease staging and grading will also occur on Days 100, 180, and 365 and at the EOT visit. If subjects withdrew due to reasons other than GVHD progression, then GVHD staging and grading will be assessed at the safety follow-up visit. Data regarding the quantification of aGVHD symptoms (extent of skin rash, total bilirubin level, volume of diarrhea) should be reported using MAGIC guidelines (Harris et al 2016); response will be assessed as per the Center for International Blood and Marrow Transplant Research (CIBMTR) modifications to the IBMTR response index as indicated in Appendix B (CIBMTR 2009, Martin et al 2009).

- Skin:
 - Only areas involved with active erythema should be used for determining body surface area staging based on the rule of nines.
 - A portion of a body area segment may be used for the quantification.
 - Desquamation or fluid-filled bullae should be reported if present as these findings are hallmarks of Stage 4 skin GVHD.
- Liver:
 - Liver GVHD staging is based solely on total (not conjugated/direct) serum bilirubin levels.
 - Liver GVHD manifesting as transaminitis without concomitant elevation in serum bilirubin should be diagnosed when the presence of GVHD is confirmed by liver biopsy (where appropriate) and scored as Stage 0.
 - If bilirubin levels were elevated before the diagnosis of GVHD in another target organ and do not increase further, then liver GVHD should not be diagnosed in the absence of biopsy confirmation. However, if hyperbilirubinemia develops at the same time or after the onset of GVHD in another target organ, then liver GVHD is presumed to be present in the absence of an identified alternative cause.

- Upper GI:
 - Symptoms of concern for upper GI GVHD include anorexia, nausea, vomiting, and dyspepsia, and assessment depends on close attention to caloric intake and symptom reporting.
 - An upper GI endoscopy should be performed whenever possible to confirm upper GI GVHD; however, the diagnosis may be made without biopsy confirmation.
 - Graft-versus-host disease is typically not considered as a possible etiology when nausea lasts fewer than 3 days or with fewer than 2 vomiting episodes per day for at least 2 days or anorexia without weight loss.
- Lower GI:
 - Staging of lower GI GVHD relies on accurate measurement of daily stool volumes and documentation of the presence of hematochezia or severe abdominal pain.
 - In cases when stool volume cannot be closely measured, volume should be calculated based on an average of 200 mL per episode multiplied by the number of episodes in 24-hour period.
 - At the time of GVHD onset, staging should be based on the highest daily volume during the 3 days before diagnosis (excluding volumes attributable to procedures such as bowel preps or endoscopy).
 - After the initiation of treatment, lower GVHD staging should be based on the diarrhea volume using (in the order of preference) the following measurements:
 1) average of 3 consecutive days, 2) average of 2 consecutive days, or 3) the volume on day of assessment.
 - Severe abdominal pain, ileus, and/or grossly bloody stool should be documented when present, because Stage 4 lower GI GVHD is staged based on the presence of these symptoms and is independent of volume of diarrhea.

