This study will include subjects who are 12 years and older as data from a Phase 1 study in pediatric subjects showed that safety of ruxolitinib was generally favorable and pharmacokinetic (PK) data were comparable to that in adults (Loh et al 2015). Adolescents between the ages of 12 and 18 years comprise approximately 5% of the adult aGVHD population, and standard treatment does not differ between adolescents and adults.

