3.1. Subject Inclusion Criteria

A subject who meets all of the following criteria may be included in the study:

- 1. Male or female, 12 years of age or older.
- Has undergone first allo-HSCT from any donor source (matched unrelated donor, sibling, haploidentical) using bone marrow, peripheral blood stem cells, or cord blood for hematologic malignancies. Recipients of nonmyeloablative and myeloablative transplants are eligible.
- 3. Clinically suspected Grades II to IV acute GVHD as per MAGIC guidelines, occurring after allo-HSCT with any conditioning regimen and any anti-GVHD prophylactic program. Biopsies should be obtained to pathologically confirm acute GVHD; in cases where a biopsy is negative, is unable to be obtained, or is clinically contraindicated, clinical suspicion of acute GVHD by the treating physician is sufficient, provided that alternative diagnoses of drug effects or infection are adequately ruled out.
- 4. Subjects with steroid-refractory acute GVHD, defined as any of the following:
 - a. Subjects with progressive GVHD (ie, increase in stage in any organ system or any new organ involvement) after 3 days of primary treatment with methylprednisolone ≥ 2 mg/kg per day (or equivalent).

- b. Subjects with GVHD that has not improved (ie, decrease in stage in at least 1 involved organ system) after 7 days of primary treatment with methylprednisolone ≥ 2 mg/kg per day (or equivalent).
- c. Subjects who previously began corticosteroid therapy at a lower dose (at least 1 mg/kg methylprednisolone) for treatment of skin GVHD or skin GVHD accompanied by upper GI GVHD, but develop new GVHD in another organ system.
- d. Subjects who cannot tolerate a corticosteroid taper, that is, begin corticosteroids at 2.0 mg/kg per day, demonstrate response, but progress before a 50% decrease from the initial starting dose of corticosteroids is achieved.
- Evidence of myeloid engraftment (eg, absolute neutrophil count [ANC] ≥ 0.5 × 10⁹/L for 3 consecutive days if ablative therapy was previously used). Use of growth factor supplementation is allowed.
- 6. Be willing to avoid pregnancy or fathering children based on 1 of the following criteria:
 - a. Women of nonchildbearing potential (ie, surgically sterile with a hysterectomy and/or bilateral oophorectomy $OR \ge 12$ months of amenorrhea).

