Appendix B. MAGIC GUIDELINES FOR STAGING AND GRADING ACUTE GVHD

Stage	Skin (Active Erythema Only)	Liver (Bilirubin)	Upper GI	Lower GI (Stool Output/Day)
0	No active (erythematous) GVHD rash	< 2 mg/dL	No or intermittent nausea, vomiting, or anorexia	Adult: < 500 mL/day or < 3 episodes/day. Child: < 10 mL/kg per day or < 4 episodes/day.
1	Maculopapular rash < 25% BSA	2-3 mg/dL	Persistent nausea, vomiting, or anorexia	Adult: 500-999 mL/day or 3-4 episodes/day. Child: 10-19.9 mL/kg per day or 4-6 episodes/day.
2	Maculopapular rash 25%-50% BSA	3.1-6 mg/dL	_	Adult: 1000-1500mL/day or 5-7 episodes/day. Child: 20-30 mL/kg per day or 7-10 episodes/day.
3	Maculopapular rash > 50% BSA	6.1-15 mg/dL	_	Adult: > 1500 mL/day or > 7 episodes/day. Child: > 30 mL/kg per day or > 10 episodes/day.
4	Generalized erythroderma (>50%) with bullae	> 15 mg/dL	_	Severe abdominal pain with or without ileus or grossly bloody stool (regardless of stool volume).

Acute GVHD Staging and Grading, MAGIC Guidelines

Overall clinical grade (based on most severe target organ involvement):

Grade 0: No stage 1-4 of any organ.

Grade I: Stage 1-2 skin without liver, upper GI, or lower GI involvement.

Grade II: Stage 3 rash and/or stage 1 liver and/or stage 1 upper GI and/or stage 1 lower GI.

Grade III: Stage 2-3 liver and/or stage 2-3 lower GI, with stage 0-3 skin and/or stage 0-1 upper GI.

Grade IV: Stage 4 skin, liver, or lower GI involvement, with stage 0-1 upper GI.

Response Definitions:

GVHD response assessments will be made with respect to changes in the organ stage relative to Study Day 1.

- Complete response (CR) is defined as a score of 0 for the GVHD grading in all evaluable organs. For a response to be scored as CR at Day 28 or later, the participant must still be in CR on that day and have had no intervening additional therapy for an earlier progression, mixed response (MR), or no response (NR).
- Very good partial response (VGPR) is defined as follows:
 - Skin: No rash, or residual erythematous rash involving < 25% of the body surface, without bullae (residual faint erythema and hyperpigmentation do not count).
 - Liver: Total serum bilirubin concentration < 2 mg/dL or < 25% of baseline at enrollment.
 - Gut:
 - Tolerating food or enteral feeding.
 - Predominantly formed stools.
 - o No overt gastrointestinal bleeding or abdominal cramping.
 - No more than occasional nausea or vomiting.

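### The flat 200 mL-per-episode conversion fits the adult lower-GI bands but fits the child bands only at 66.7-70 kg, so child-column subjects with unmeasured stool can have two stages from one record

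*Protocol*

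**What the plan says.** Protocol 7.6.1 (Lower GI) bases staging on stool volume. When volume is not reliably available, "volume should be calculated based on an average of 200 mL per episode multiplied by the number of episodes in 24-hour period". No version for children or per kilogram is given.

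Appendix B, repeated in SAP Appendix B, stages lower GI on volume or episode count, with separate adult and child bands:

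- Stage 0: "Adult: < 500 mL/day or < 3 episodes/day. Child: < 10 mL/kg per day or < 4 episodes/day"
- Stage 1: "Adult: 500-999 mL/day or 3-4 episodes/day. Child: 10-19.9 mL/kg per day or 4-6 episodes/day"
- Stage 2: "Adult: 1000-1500mL/day or 5-7 episodes/day. Child: 20-30 mL/kg per day or 7-10 episodes/day"
- Stage 3: "Adult: > 1500 mL/day or > 7 episodes/day. Child: > 30 mL/kg per day or > 10 episodes/day"

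Neither document gives an age or weight at which the child bands apply, or says which of the two measures takes precedence when volume is missing. Adolescents are eligible (Protocol 3.1: "Male or female, 12 years of age or older"). Protocol 1.3.2 adds that "Adolescents between the ages of 12 and 18 years comprise approximately 5% of the adult aGVHD population".

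Response is scored from the change in organ stage since Day 1. A one-stage improvement in one organ, with no progression elsewhere, is a PR.

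**The concern.** A fixed volume per episode cannot track bands that scale with body weight. A subject staged on the child column without measured stool can be staged directly on the episode count or on the converted volume. At most weights some counts give different stages.

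Because one stage in one organ is enough for PR, the choice of rule can decide whether that subject counts towards Day 28 ORR. It can also decide CR, which needs stage 0 in every organ. If the rule changes between Day 1 and a later visit, a stage change can appear with no change in stool. The trial is open-label and single-arm, and standardized criteria are the only measure that Protocol 4.2 offers against bias, so these criteria should give one answer per record.

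**Working it through.** **Inputs.** 200 mL per episode (Protocol 7.6.1); adult and child bands (Appendix B); 70 subjects (Protocol 4.3.1); 5% adolescents (Protocol 1.3.2). Body weight is an assumption, shown as a range, because the documents give none for adolescents. Values between 19.9 and 20 mL/kg are treated as stage 1.

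**Step 1: adult column.** Volume = 200 × n.

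- 2 episodes = 400 mL, stage 0 by both measures
- 3-4 = 600-800 mL, stage 1 by both
- 5-7 = 1000-1400 mL, stage 2 by both
- 8 = 1600 mL, stage 3 by both

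There is no mismatch at any whole daily count from 0 to 15.

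**Step 2: what the child column needs.** Let v be mL/kg per episode. The two measures agree at every count only if all of these hold:

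- 3v < 10 and 6v < 20, so v < 3.33
- 4v ≥ 10, so v ≥ 2.50
- 7v ≥ 20, so v ≥ 2.86
- 10v ≤ 30, so v ≤ 3.00
- 11v > 30, so v > 2.73

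The binding limits are 2.86 ≤ v ≤ 3.00. With v = 200 / weight, weight must lie between 200/3.00 = 66.7 kg and 200/2.857 = 70 kg.

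**Step 3: mismatches by weight.** Converted volume = 200 × n / weight, for 1-12 episodes a day.

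| Weight (assumed) | Counts that differ | Which counts | Direction of the conversion |
|---|---|---|---|
| 35 kg | 9 | 2-10 | higher; two stages at 6 episodes (34.3 mL/kg: 3 vs 1) |
| 40 kg | 9 | 2-10 | higher by one stage |
| 45 kg | 7 | 3, 5-10 | higher by one stage |
| 50 kg | 6 | 3, 5, 6, 8-10 | higher by one stage |
| 60 kg | 3 | 3, 6, 10 | higher by one stage |
| 66.7-70 kg | 0 | none | agrees |
| 80 kg | 3 | 7, 11, 12 | lower by one stage |

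Worked examples at 45 kg: 3 episodes = 600/45 = 13.3 mL/kg (stage 1, against 0 by count); 5 = 22.2 (2 against 1); 7 = 31.1 (3 against 2). At 80 kg, 7 episodes = 17.5 mL/kg (1 against 2).

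**Step 4: response with one rule at both visits.** At 50 kg, lower GI only:

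| Day 1 to later visit | By count | By converted volume |
|---|---|---|
| 7 to 5 episodes | 2 to 1, improved | 28 to 20 mL/kg, 2 to 2, not improved |
| 8 to 7 episodes | 2 to 2, not improved | 32 to 28 mL/kg, 3 to 2, improved |
| 4 to 3 episodes | 1 to 0, cleared | 16 to 12 mL/kg, 1 to 1, not cleared |

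Over all pairs with 4-14 episodes at baseline and 0-14 at follow-up (11 × 15 = 165), the improved/not-improved result differs in 19 pairs at 45 kg (11.5%) and 20 at 50 kg (12.1%). Each pair has equal weight, so this is a share of possible records and not a probability for a patient.

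**Step 5: response with a switch of rule.** At 50 kg, 5 episodes at both visits is stage 2 by volume (20 mL/kg) and stage 1 by count. Volume on Day 1 and count on Day 28 shows a one-stage improvement; the reverse order shows a one-stage deterioration.

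**Step 6: exposure.** 0.05 × 70 = 3.5 subjects, or 3.5/70 = 5 percentage points of ORR as an upper limit.

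**The case against.** **The child column may not apply.** Protocol 1.3.2 treats adolescents as part of the adult acute GVHD population. If everyone aged 12 or over is staged as an adult, the conflict disappears. This stands as a condition, but the plan does not say so, and it prints child bands that would then have no user.

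**7.6.1 already picks converted volume.** Read strictly, a site without measured stool converts at every visit, and no switch occurs. Most pairs then give the same result under either rule: 146 of 165 at 45 kg and 145 of 165 at 50 kg. That limits the effect. It does not remove it, because Appendix B still offers the episode count as an alternative without ranking the two. The study reference manual, which Protocol 6 cites for details, might settle this, but it is not among the documents.

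**CR is less affected than it may seem.** A reader might infer that CR is in doubt for anyone with three or fewer stools. At 45 kg only exactly 3 episodes is in dispute; 1 and 2 are stage 0 by both measures. Losing CR also need not change ORR, which counts VGPR and PR too, and the VGPR gut criteria do not use the stage.

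**The adult match is not perfect.** 7.6.1 prefers three-day means once treatment has started. Eight episodes in three days is 533 mL/day (stage 1) but 2.67 episodes a day (stage 0). Twenty-two in three days is 1467 mL/day (stage 2) but 7.33 episodes a day (stage 3). The adult agreement is therefore claimed for whole daily counts only.

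**Conclusion.** The conflict between 7.6.1 and Appendix B is real. For child-column subjects, the flat conversion and the episode bands agree only at 66.7-70 kg. Below that range the conversion stages higher, by two stages at some counts at about 35 kg or less. Above it, the conversion stages lower. It would be wrong to infer that heavier adolescents are unaffected.

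The effect on the trial is small. It reaches at most about 3-4 of 70 subjects, if the 5% figure carries over to enrolment, and among them only those with lower-GI disease, no measured volume, child-column staging and a discordant count.

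A reader might go on to infer an inflated Type I error. If one or two nonresponders were always counted as responders at the 37-responder cut-off, with the interim rule unchanged, the stated 0.0189 would become 0.032 or 0.051. The documents do not support this as a forecast. It needs one or two favourable reclassifications among about 3.5 adolescents, nothing in the plan gives such a rate, and errors in the other direction would lose responders. The point rests on the ambiguity in scoring the primary endpoint, not on that range.

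**What to change.** Reconcile Protocol 7.6.1 with Appendix B, and carry the same wording into SAP Appendix B:

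1. Limit the 200 mL conversion to subjects staged on the adult column.
2. Stage child-column subjects without measured volume on the existing Appendix B episode bands. Alternatively, use a per-kilogram conversion that reproduces those bands, which means a value from 2.86 to 3.00 mL/kg per episode.
3. State which subjects use the child column, by age or weight.
4. Use the same method for each subject on Day 1 and at every later response visit.

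The cost is a few sentences in 7.6.1 and a matching note in the SAP. No new data are needed: episode counts already feed the present conversion, and body weight is recorded with the vital signs.
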